1.0 Study Summary

Study Title	Hiatal Hernia Repair Using SurgiMend Mesh at the hiatus: A Pilot Study				
Study Design	
Prospective, single-arm, open-label study to evaluate re-occurrence and quality of life in subjects undergoing primary Hiatal hernia repair using SurgiMend biological mesh. Up to 15, with a target of 10, subjects are planned to be enrolled at one site. All subjects will receive the SurgiMend mesh during surgery. Data collected will be compared to historical data.
 
Subjects will complete a pre-operative visit. After surgery, in addition to any standard of care visits, subjects will complete 3- and 6-month follow-ups involving a phone QOL survey and will have an upper GI series at 6 months.
				
Primary Objective	Recurrence rates of hiatal hernia as compared to historical rates				
Secondary Objective(s)	To evaluate quality of life of patients in which SurgiMend mesh was used during Hiatal hernia surgery using the GERD-HRQL, compared to historical data.				
Research Intervention(s)/ Investigational Agent(s)	Assessment of recurrence rates of hiatal hernias following use of SurgiMend mesh compared to historical rates				
IND/IDE #	N/A				
Study Population	Patients having a planned hiatal hernia repair				
Sample Size	Up to 15, target of 10				
Study Duration for individual participants	7 to 8 months (6 months post-surgery, plus up to 45 days prior to surgery)				
Schedule of Assessments	Visit	Pre-op/ baseline (w/in 45 days pre-op)	1-2 Week SOC follow-up (±2 weeks)	3 Month Follow- up (±2 weeks)	6 Month Follow-up (±2 weeks)
	Informed Consent	X			
	Verify Eligibility Criteria	X			
	Quality of Life (QoL)* Questionnaire	X		X	X
	Upper GI				X
	AE Assessment*	X	X	X	X
	Vitals, Labs, EKG	X	X		

	*QoL and AE assessment can be done via phone call. Questionnaire used is the GERD Health-Related Quality of Life Questionnaire (GERD-HRQL)
Study Specific Abbreviations/ Definitions	Quality of Life: (QOL); Gastroesophageal reflux disease (GERD); Upper gastrointestinal tract radiography (UGI); Gastroesophageal Reflux Disease-Health Related Quality of Life (GERD-HRQL), Adverse Event (AE); Standard of Care (SOC)

2. Objectives*

- 2.1. Study recurrence rates of hiatal hernias after use of SurgiMend mesh compared to historical rates. As available, recurrence rates will be compared to historical rates with and without using mesh for hernia repair.
- 2.2. Assess the quality of life status post laparoscopic hiatal hernia repair with SurgiMend Mesh compared with historical rates as available

3. Background

- 3.1. Hiatal hernia repair is a surgical procedure with a well-recognized high recurrence rate of 25.5 % up to 50% and low post-op satisfaction and quality of life (1-3). Literature suggests that follow up imaging for evaluation of repair does not generally occur until 1 year post operatively with little data on when the recurrence actually occurred (1-3). Biologic mesh has been studied as a possible adjunct in these surgeries to decrease recurrence and increase QOL. However, there are very few studies that have examined the actual recurrence rate following the use of mesh to reinforce the hiatal hernia repair. We wish to study the efficacy of surgical mesh (Surgimend) for use in hiatal hernia repair to decrease recurrence and increase QOL
- 3.2. Currently, there is conflict in the literature as to the best type of surgical procedure to be performed and there is little overall literature about the use of bovine dermis product used in hernia repair to reduce recurrence rate and QOL improve with the addition of mesh for a laparoscopic hiatal hernia repair. There is some evidence that bovine dermis has the ability to adjust to the pressure points and is less likely to pull apart and tear under pressure. This results in a decrease in mesh erosion ultimately resulting in less complications, including fewer recurrences. (4)

4. Study Endpoints

- 4.1. Primary Endpoint: Recurrence of hiatal hernia as assessed by upper GI and clinical evaluation.
- 4.2. Secondary Endpoint: Quality of life as marked by GERD symptoms on GERD-HSQL (5)

5. Study Intervention/Investigational Agent

- 5.1. Description: SurgiMend Mesh -FDA approved noncross-linked bovine dermis biologic mesh
- 5.2. SurgiMend Mesh will be used according to FDA approved recommendations for the use of abdominal wall hernia reinforcement
- 5.3. SurgiMend is intended for implantation to reinforce soft tissue where weakness exists and for surgical repair of damaged or ruptured soft tissue membranes. SurgiMend is specifically indicated for:
 - 5.3.1. Hernia repair including abdominal, inguinal, femoral, diaphragmatic, scrotal, umbilical, and incisional hernias.

6. Procedures Involved

- 6.1. Intervention: Following placement of SurgiMend mesh during laparoscopic hiatal hernia repair, patient will be scheduled for follow up using an upper GI series to check for recurrence of the hiatal hernia. Follow up upper GIs will be performed at 6 months post-surgery. Subjects will also complete a QOL survey to assess other GI associated symptoms before and after surgical repair. The QOL survey and AE assessment can be administered by phone by study team members

6.2. Study Calendar:

Visit	Pre-op/ baseline (within 45 days of procedure)	1-2 Week SOC follow- up (±2 weeks)	3 Month Follow-up (±2 weeks)	6 Month Follow-up (±2 weeks)	Medical Records review throughout 6 month follow up
Informed Consent	X				
Verify Eligibility Criteria	X				
Quality of Life (QoL) Questionnaire	X		X	X	
Upper GI				X	
AE Assessment	X	X	X	X	X
Vitals, Labs, EKG	X	X			X

- 6.3. Patients having hiatal hernia repair performed by [name], who is the PI for the study, will have Surgimend mesh placed as per the SurgiMend approved use.
- 6.4. [name] and/or surgical residents who are named as study team members will introduce and explain the study to the patient. If the patient is interested, they will be provided with a copy of the complete informed consent form and one-page summary of the study. A research coordinator will follow up with the patient by phone. If a patient decides to participate, informed consent will be obtained by a member of the

study team in the office prior to surgery or a coordinator will call the patient to ensure patient understanding and desire to proceed with enrollment in study prior to the day of surgery by completing telephone consent. For remote consent, telephone consent will be utilized, with two team members verifying consent and documenting on the ICF. A copy of the ICF will also be emailed or mailed to the subject to sign as well. The subject will then return the sign copy, via scan, fax, picture, or return hard copy via mail or next in-person visit and will be filed with the consent completed by 2-person verification. A research coordinator will confirm eligibility prior to the patient being enrolled in the study.

- 6.5. After informed consent is obtained and eligibility is confirmed, the patient will answer the GERD-HRQL survey (please see 6.8.2 for details on the survey) prior to the day of surgery.
- 6.6. The patient will then undergo the planned elective procedure for hiatal hernia repair. Following the procedure, they will be admitted and observed in the hospital per standard of care. After discharge, the patient will be seen in the office for a standard of care follow up visit 1 to 2 weeks after discharge. The patient will complete the same QOL survey at 3 and 6 months as well as have a fluoroscopic Upper GI with contrast at 6 months to check for radiographic recurrence as outlined below. The research coordinator may administer the survey by telephone
- 6.7. The research procedures for this study include UGI and QOL survey
 - 6.7.1. UGI is a procedure that uses a fluoroscopic x-ray examination with the use of an orally ingested barium-based or other contrast material (as determined by the radiologist performing the test) to visualize the esophagus, stomach, and duodenum. This is a non-invasive test to identify abnormalities in the digestive tracts, including hiatal hernias (6).
 - 6.7.2. UGI Risks –
 - 6.7.2.1. Exposure to radiation (6mSv) is comparable to 2 years of background radiation
(<https://www.radiologyinfo.org/en/info.cfm?pg=safety-xray>)
 - 6.7.2.2. Approximately ¼ the exposure of a CT
 - 6.7.2.3. allergic reaction to contrast material
 - 6.7.2.4. constipation/obstruction from incomplete passage of the contrast agen
 - 6.7.3. QOL survey: GERD-HRQL
 - 6.7.3.1. The GERD-HRQL was initially developed to measure the typical symptoms of GERD and their effect on a patient's quality of life. It was initially determined to have face validity and subsequent studies assessed its content validity and criterion validity. Reliability was determined by the test-retest

method. This instrument is practical, with little administrative burden and has been validated for use via the telephone call (5).

6.7.3.2. Because this QOL survey is directly tied to how a patient's gastrointestinal (GI) symptoms impact their quality of life, there is little risk for undue psychological harm or emotional distress experienced by the patient.

6.8. Recurrence rate will be analyzed by a UGI done 6 months postoperatively in conjunction with patient's reported physiological assessment per the GERD-HRQL. As indicated, the physician reviewing this information will follow up with patient to ensure proper care and future treatment.

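### The 6-month recurrence rate is to be compared with historical rates of unspecified timing, drawn from a literature that the protocol says is generally not imaged before 1 year; on timing alone this tends to favour the mesh.

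*Combined protocol and SAP*

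**What the plan says.** The primary objective in the Study Summary (1.0) is "Recurrence rates of hiatal hernia as compared to historical rates". There is no concurrent control, so history is the only comparator. Section 2.1 divides the historical rates by use of mesh but not by follow-up time: "As available, recurrence rates will be compared to historical rates with and without using mesh for hernia repair".

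Section 6.1 fixes this study's imaging: "Follow up upper GIs will be performed at 6 months post-surgery". Section 6.8 makes that film the basis of the analysis: "Recurrence rate will be analyzed by a UGI done 6 months postoperatively in conjunction with patient's reported physiological assessment per the GERD-HRQL". Participation ends 6 months after surgery (1.0), and no later film is planned.

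The historical figures are in Background (3.1), which describes a "well-recognized high recurrence rate of 25.5 % up to 50" per cent. Its next sentence, with the same references (1 to 3), says that "follow up imaging for evaluation of repair does not generally occur until 1 year post operatively", and adds "with little data on when the recurrence actually occurred".

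Section 17.1 calls the analysis descriptive because of the small sample and makes the historical comparison optional. It gives no method and no rule for choosing comparators.

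**The concern.** A recurrence proportion has meaning only with a follow-up time attached. This study counts recurrences over 6 months. The literature it cites generally counts them over a year or more. A patient who recurs at month 9 is a success here and a failure in a series imaged at 12 months.

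A lower rate in this study could therefore reflect a shorter observation window, a mesh effect, or both, and this study's data could not separate them because follow-up stops at 6 months. A confidence interval would not reveal the problem, and more patients would not remove it. What is at stake is the reading of the only primary comparison, in a protocol whose stated interest (3.1) is whether the mesh reduces recurrence.

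**Working it through.** The documents contain no sample-size or power calculation, so there is no planned figure to reproduce. The check asks how often an inert mesh would give an observed rate below the historical one.

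**Inputs from the protocol**
- Historical rate p: 25.5% and 50%, no time attached (3.1).
- Imaging in this study: one upper GI series at 6 months (6.1, 6.8).
- Sample size: target 10, maximum 15 (1.0, 12.1).

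**Assumptions, not in the documents**
- A recurrence, once present, stays countable.
- The share f of recurrences present by 6 months is varied, because the protocol says that timing data are scarce.
- In one scenario the hazard is constant and p is a 12-month rate.

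**Step 1: direction.** With no mesh effect, the 6-month rate is p6 = f × p with f ≤ 1. So p6 ≤ p, with equality only if every recurrence is present by 6 months.

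**Step 2: no-effect 6-month rates.**
- f = 0.90: 0.90 × 25.5% = 22.95%; 0.90 × 50% = 45%.
- f = 0.75: 0.75 × 25.5% = 19.1%; 0.75 × 50% = 37.5%.
- Constant hazard: p6 = 1 − (1 − p)^(6/12). For 25.5%, 1 − √0.745 = 13.7%. For 50%, 1 − √0.5 = 29.3%.

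**Step 3: chance of an observed rate below the historical rate, n = 10.** Below 25.5% means 2 or fewer recurrences (2/10 = 20%, 3/10 = 30%). Below 50% means 4 or fewer. The probabilities are exact binomial.

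| Recurrences present by 6 months | p6 (from 25.5%) | P(X ≤ 2) | p6 (from 50%) | P(X ≤ 4) |
|---|---|---|---|---|
| All (no bias) | 25.5% | 51% | 50% | 38% |
| 90% | 22.95% | 59% | 45% | 50% |
| 75% | 19.1% | 70% | 37.5% | 69% |
| Constant hazard, 12-month p | 13.7% | 85% | 29.3% | 86% |

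**Step 4: n = 15.** In the same row order, the chances are 44%, 54%, 68% and 86% against 25.5% (3 or fewer), and 50%, 65%, 84% and 96% against 50% (7 or fewer). The larger sample does not remove the effect.

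**Step 5: precision.** The exact 95% interval is 0.3% to 44.5% for 1 recurrence in 10, and 6.7% to 65.2% for 3 in 10.

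**The case against.** The strongest reply is that the protocol never names 25.5% to 50% as its comparator. The range appears in Background as motivation, and the objectives say only that historical rates will be used as available. A time-matched series is neither required nor excluded. This stands: a reader might infer that the plan commits itself to testing the 6-month rate against 25.5% to 50%, and the text does not say so. But these are the only historical figures given, and nothing steers the investigator away from them.

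Second, the protocol acknowledges that the timing of recurrence is poorly known, and 6-month imaging might be meant to help fill that gap. The protocol does not say this. If it were the aim, it would justify reporting an early recurrence rate, not setting that rate against later ones.

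Third, the size is not known. If nearly all recurrences are present by 6 months, the bias is close to zero. No time is attached to the historical figures, and the statement about 1 year is qualified as general. This stands in full.

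Fourth, timing is only one difference from the historical series. Completeness of imaging, the definition of recurrence and the restriction to type 3 or 4 hernias (10.1.1.1) may also differ, in directions the documents do not describe. The net bias is therefore unknown, and the claim here is limited to timing.

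Fifth, this is a descriptive pilot with no test, threshold or decision rule. That lowers the severity. It does not dispose of the point, because 1.0 makes the comparison the primary objective and its Study Design row states without qualification that it will be made, although 17.1 makes it optional.

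**Conclusion.** The point holds in limited form. The comparator's time point is unrestricted, the protocol's own account places the cited literature's imaging generally at 1 year or later, and this study's only film is at 6 months. On timing alone, the comparison would tend to favour the mesh even if it had no effect.

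The size is illustrative. At n = 10 the chance that an inert mesh falls below 25.5% runs from 51% (no bias) to 85% (constant hazard, 25.5% as a 12-month rate), depending on a share that the documents do not give.

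Two stronger readings are tempting. One is that an inert mesh would show a definite relative reduction, such as the 46% (1 − 13.7/25.5) or 41% (1 − 29.3/50) that the constant-hazard case implies. The documents give no recurrence curve and no time for the historical figures, so neither number is an estimate of the bias. The other is that an error rate is inflated. No test is planned, so no stated error rate is wrong; the problem lies in the comparison and its interpretation.

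Severity: should be fixed before results are interpreted.

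**What to change.** In 1.0, 2.1 and 17.1, define the endpoint as 6-month (early) recurrence, with 4.1 worded to match. Limit any numerical comparison to historical series with systematic contrast imaging at about 6 months, and list the series in a short table with imaging time, imaging method and recurrence definition.

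If no such series is found, report the 6-month rate with an exact confidence interval. State that no reduction will be claimed against rates imaged at 1 year or later, including the 25.5% to 50% range in 3.1.

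The cost is protocol wording and a brief literature tabulation, with no added patients or procedures. The downside is a more modest claim, and possibly no matching comparator.

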 - 15.2.1.3. Reaction to the barium or other contrast material include allergic reaction, constipation/obstruction from incomplete passage of the contrast agent. Patients will be instructed to drink plenty of fluids following the procedure to mitigate risk of constipation and obstruction
- 15.3. Risk of allergic reaction to bovine mesh is approximately 3% in the general population (6,7).
- 15.4. The overall risk of psychological impact of QOL survey is minimal. This survey was designed to specifically assess the impact of GI symptoms on a patient's quality of life. Therefore, there is a minimal psychological impact as patients have already been enduring GI side effects from the hiatal hernia, including heartburn, pain, and reflux.

16.Potential Benefits to Subjects*

- 16.1.1. Subjects may or may not benefit. Subjects may experience reduction in recurrence of hiatal hernia as well as improved QOL.

17.Data Management* and Confidentiality

- 17.1. Due to the low number of patients expected to be enrolled, statistical analysis will be descriptive in nature. Recurrence rates and QOL means may be compared to historical controls.
 - 17.1.1. Data to be collected: Demographics, vitals, surgical history, medications, recurrence of hernia, comorbidities, dysphagia and reflux symptoms, results of UGI for presence/absence of recurrence of hiatal hernia and labs including a complete blood count (CBC), complete metabolic panel (CMP), and an EKG, which are all standard of care for this procedure.

18.Provisions to Monitor the Data to Ensure the Safety of Subjects*

- 18.1. Standard of care monitoring and follow-up; 24 hour patient accessibility to a physician; hospital follow-up phone call week of surgery per hospital protocol; phone interview by a member of the study team at 3 and 6 months. Surgeon will be informed of and handle any potentially adverse events related to the study or surgical procedure.

19.Provisions to Protect the Privacy Interests of Subjects

- 19.1. Data will be encrypted and stored in a password protected shared drive accessible to study personal listed. Only de-identified information will be shared with sponsor and statistician.

20.Compensation for Research-Related Injury

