- 20.1. While the surgical procedure is considered greater than minimal risk, there is not an increase in risk using the SurgiMend mesh compared to other types of surgical mesh. The patient will receive the usual perioperative care and SurgiMesh regardless of whether participating in the study. There is no compensation set aside for injury while on study.

21.Economic Burden to Subjects

- 21.1. No anticipated additional economic burden will be placed on the participants as they will receive standard of care for surgery. They will be compensated as described in section 13.4.

22.Consent Process

- 22.1. See above – section 13; patient will receive education about the study during their doctor visit and given a consent and study summary to take home and read. When the patient returns, study questions will be answered and if willing to participate, patient will sign the consent. Alternatively, a member of the study team will call the patient to review the study and obtain informed consent over the phone. In such cases, the patient will sign consent documents on the day of surgery or the consent will be signed and documented by two study coordinators.

23.Setting

- 23.1. See section 13 for more detail. Patients will be introduced to study at physicians office. They will have surgery per standard of care at a KHN facility, followed by an SOC follow up office visit with the surgeon 1 to 2 weeks post-surgery. They will receive a phone call at 3 months and 6 months to fill out the GERD-HRQL and will travel to a KHN facility of their choice to have an abdominal X-Ray performed at the 6 month time points.

24.Resources Available

- 24.1. Physician has allocated time for research; residents are required to have research done prior to graduation.

25.Multi-Site Research*

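### The primary recurrence result is not tied to a reading of the 6-month upper GI made without the symptom score, so it is open to assessor bias in either direction

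*Combined protocol and SAP*

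**What the plan says.** - **Design (section 1.0).** The study is described as "Prospective, single-arm, open-label study to evaluate re-occurrence and quality of life". Every subject receives the mesh, and comparison is with historical data.
- **Primary endpoint (4.1).** "Recurrence of hiatal hernia as assessed by upper GI and clinical evaluation". The section gives no rule for combining the two components.
- **How recurrence is analysed (6.8, first sentence).** "Recurrence rate will be analyzed by a UGI done 6 months postoperatively in conjunction with patient's reported physiological assessment per the GERD-HRQL".
- **What follows (6.8, second sentence).** "As indicated, the physician reviewing this information will follow up with patient to ensure proper care and future treatment". The physician's role is not given.
- **Secondary endpoint (4.2).** Quality of life measured by the same GERD symptom questionnaire.
- **Operating surgeon (6.3).** Patients are those whose repair is done by the surgeon "who is the PI for the study, will have Surgimend mesh placed as per the SurgiMend approved use".
- **Radiologist (6.7.1, 6.8.1.3).** Contrast is chosen "as determined by the radiologist performing the test", and the radiologist decides whether a pregnancy test is needed. The radiologist is given no stated role in the endpoint.
- **Place of the exam (23.1).** For the 6-month imaging, patients "will travel to a KHN facility of their choice".
- **Data items (17.1.1).** The list includes recurrence of hernia, dysphagia and reflux symptoms, and, as its own item, "results of UGI for presence/absence of recurrence of hiatal hernia".

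**The concern.** The UGI is the only objective efficacy measure in the study. Read literally, 4.1 and 6.8 allow the symptom score and a clinical opinion into the recurrence call itself. The secondary endpoint then becomes part of the primary one, and the two can no longer be read as separate evidence.

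The errors can run both ways. An anatomical recurrence in a patient without symptoms may be called absent. Reflux in a patient with an intact repair may be called recurrence. Because treatment is known to everyone and the surgeon who did the repair leads the study, expectation can influence equivocal cases, and nothing in the plan would let a reader detect that afterwards. At stake is the credibility of the numerator of the recurrence rate, whose comparison with historical rates is the primary objective.

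**Working it through.** The plan states no power, alpha or target rate, so there is no figure of its own to reproduce. The check has two parts.

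**1. The passages side by side**

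| Question | What the documents give |
|---|---|
| What counts as the result? | UGI plus clinical evaluation (4.1); UGI with GERD-HRQL (6.8); radiographic recurrence as the purpose of the UGI (6.6); UGI presence/absence and recurrence of hernia as two items (17.1.1) |
| Which item is analysed? | Not stated |
| Who makes the call? | Not stated; 6.8 mentions a reviewing physician only in connection with follow-up |
| Is the film read without the symptom score? | Not stated; 6.8 points towards joint review |
| May a radiology finding be reclassified? | Not addressed |
| Any blinding or independence elsewhere? | 19.1 covers de-identified data sent to the sponsor and statistician, not the reading of images |

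**2. The weight of one reading**

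Inputs: target n = 10 and maximum n = 15 (1.0, 12.1); lowest historical rate 25.5%, highest 50% (3.1). All subjects are assumed to have a 6-month UGI. One changed reading moves the rate by 1/n:

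- n = 10: 1/10 = 10.0 percentage points
- n = 15: 1/15 = 6.7 percentage points

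Around the 25.5% figure, with exact (Clopper-Pearson) 95% intervals:

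| n | Recurrences | Rate | 95% CI |
|---|---|---|---|
| 10 | 3 | 30.0% | 6.7% to 65.2% |
| 10 | 2 | 20.0% | 2.5% to 55.6% |
| 15 | 4 | 26.7% | 7.8% to 55.1% |
| 15 | 3 | 20.0% | 4.3% to 48.1% |

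At either sample size one reading can put the point estimate on the other side of 25.5%. All four intervals contain 25.5%.

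**Sensitivity to direction.** Assume a true rate of 30%. Let m be the share of true recurrences called absent and f the share of intact repairs called recurrent. Both are assumptions; the documents give neither. The expected observed rate is 0.30(1 − m) + 0.70f. The last two columns give the binomial probability of an observed rate below 25.5%, that is at most 2 of 10 or at most 3 of 15.

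| m | f | Expected observed rate | n = 10 | n = 15 |
|---|---|---|---|---|
| 0 | 0 | 0.30 | 38% | 30% |
| 0.10 | 0 | 0.27 | 47% | 39% |
| 0.20 | 0 | 0.24 | 56% | 50% |
| 0.20 | 0.086 | 0.24 + 0.06 = 0.30 | 38% | 30% |
| 0.20 | 0.10 | 0.24 + 0.07 = 0.31 | 36% | 27% |

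The cancelling value in the fourth row is f = 0.06/0.70 = 0.086. Under-calling alone shifts the result noticeably, but a modest rate of over-calling removes the shift or reverses it.

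**The case against.** The strongest case on the other side has four parts.

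**The plan already separates the UGI result.** Section 17.1.1 records UGI presence/absence apart from symptoms and from recurrence of hernia, and 6.6 gives radiographic recurrence as the purpose of the exam. This stands, and it makes the repair easy. It does not settle the matter, because no passage says which item enters the analysis, and 4.1 and 6.8 point to a combined call.

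**The analysis is descriptive.** Section 17.1 says so and makes the historical comparison optional. No decision turns on 25.5%, and with intervals this wide a single film does not change any inference. This stands and limits the severity.

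**The direction is unknown.** This also stands. The table above shows that the 56% and 50% figures hold only if errors run one way.

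**The exam is live fluoroscopy.** The radiologist may meet the patient and hear about symptoms, so a fully symptom-blind reading cannot be guaranteed. This stands as a limit on the remedy. The study questionnaire itself can still be withheld.

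Two stronger readings are tempting, and the documents support neither. A reader might infer from 6.8 that the operating surgeon, or one reviewing physician, makes or overrides the recurrence call. The sentence is about follow-up care; it does not identify that physician as the PI or as the endpoint assessor. A reader might also infer that the study team controls what the radiologist is told, because it schedules the exam. Section 6.8.1.1 says only that a team member books through central scheduling, and no passage describes the content of the request.

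**Conclusion.** The concern holds in a limited form. As written, 4.1 and 6.8 bring clinical evaluation and the secondary endpoint into the primary recurrence result, and nothing fixes the assessor, the analysed item or a reading made without the symptom score. The recurrence rate is therefore open to assessor bias in either direction. Each changed reading is worth 10.0 points at n = 10 or 6.7 points at n = 15, assuming every subject has a 6-month UGI.

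The documents do not show that bias will occur, which way it would run, or that the PI decides the endpoint. No error rate or stopping decision is affected. What is affected is how far the reported rate, and any comparison with historical rates, can be trusted. The change is worth making in a pilot of this size because it is cheap, but it is not a fatal flaw.

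**What to change.** Amend 4.1, 6.8 and 17.1.1 together. Changing only the last two would leave 4.1 contradicting them.

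1. State that the recurrence result in the primary analysis is the presence/absence finding in the signed report of the radiologist who performs the 6-month UGI.
2. State that this report is made without access to the study GERD-HRQL, and that neither the operating surgeon nor the study team may reclassify it for the analysis.
3. Report clinical evaluation and GERD-HRQL as separate variables, and tabulate their agreement with the UGI result so that discordant cases are visible.
4. Record the facility and the contrast used for each exam. The choice of contrast stays with the radiologist, as now.

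**Cost.** Protocol wording and two recorded items. No extra reader or procedure is needed, because a radiologist already performs each exam. The downside is that the radiologist reports without the symptom score, and what the patient says during the exam cannot be fully withheld. The surgeon keeps all information for patient care.
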